2.5.5 Handling of missing values/censoring/discontinuations

Time to event (MCI due to AD or dementia due to AD), Time to first change in diagnosis classification and Time to first decrease in RBANS total \geq 14 points

In general, an observation will be censored if no event has been observed at the TTE analysis cut-off date. The censoring date will be defined as the last date (before cut-off date) where the TTE endpoint has been assessed.

The censoring date for each participant that did not have an event (i.e., a confirmed diagnosis) is defined as follows:

1. For participants ongoing in the study without a confirmed diagnosis at the time of the cut-off: the last day of a diagnosis assessment (the previous visit where a diagnosis assessment occurred prior to the cut-off date).
2. For participants who permanently discontinued from the study prior to the cut-off: The last day of a diagnosis assessment prior to study discontinuation.
3. For participants who had their last diagnosis assessment prior to randomization (i.e. during screening epoch) or do not have any diagnosis assessment post randomization, their randomization date will be used as censoring date.
4. For analysis of time to first decrease in RBANS \geq 14 points, the last RBANS assessment date will be used as censoring date instead of last diagnosis assessment date mentioned in above three points.

Note: For Time to MCI due to AD or dementia due to AD, the cut-off date will be 25 August 2019. Analysis of Time to First change in diagnosis classification, the cut-off date will be database lock date, additional analysis of time to first change in diagnosis classification will be performed for participants on treatment. Also time to first decrease in RBANS \geq 14 points will be performed for participants on treatment.

Further details on derivation of events and censoring will be added to the programming document specifications (PDS).

Other primary efficacy endpoint variable (APCC)

Due to the early termination of the trial, analyses of primary efficacy variable APCC will in general be based on observed cases only, i.e. there will be no imputation of missing data. Exception in primary efficacy variable APCC applies to missing data in subtests of Raven's matrices included in the primary efficacy variable APCC. Missing values for the subtests of Raven's matrices of the APCC may be imputed using the imputation rule defined in [Appendix 5.1.3.3.1](#).

2.5.6 Supportive analyses

Not Applicable.

2.6 Analysis of the key secondary objective

2.6.1 Key secondary endpoint

The key secondary endpoint variable is CDR-SOB.

Clinical Dementia Rating (CDR) global and Sum of Boxes (CDR-SOB)

The CDR is obtained through semi-structured interviews of participants and informants, and cognitive functioning is rated in six domains: memory, orientation, judgment and problem solving, community affairs, home and hobbies, and personal care. Each domain is rated on a 5-point scale of functioning as follows: 0, no impairment; 0.5, questionable impairment; 1, mild impairment; 2, moderate impairment; and 3, severe impairment (personal care is scored on a 4-point scale without a 0.5 rating available). The CDR global score ranges from zero to three, with greater scores indicating greater disease severity. The CDR-SOB is defined as the sum of the ratings from the six domains, ranging from 0 to 18 with a minimum increment of 0.5. A higher CDR-SOB score indicates greater disease severity.

2.6.2 Statistical hypothesis, model, and method of analysis

The key secondary objective aimed to evaluate effects of CNP520 versus Placebo by comparing changes from baseline to Month 60. Due to the early termination of CNP520, no data have been collected at Month 60. Only very few participants have provided data on active treatment with CNP520 beyond one year of follow-up. Hence, the originally planned inferential and model based statistical analyses cannot be performed and are no longer applicable.

Tables

CDR-SOB and CDR global will be summarized on the SAF.

2.6.3 Handling of missing values/censoring/discontinuations

Due to early termination of the trial, analyses of CDR-SOB will be based on observed cases only, i.e. there will be no imputation of missing data.

2.7 Analysis of secondary efficacy objective(s)

2.7.1 Secondary endpoints

RBANS Total score and Index scores

The RBANS is comprised of the following five neurocognitive domains, with associated subtests used for Index scores:

- Immediate Memory – List Learning and Story Memory (IMI)
- Visuospatial/Constructional – Figure Copy and Line Orientation
- Language – Picture Naming and Semantic Fluency
- Attention – Digit Span and Coding
- Delayed Memory – List Recognition and Sum of (List Recall, , Story Recall, and Figure Recall; DMI)

The RBANS generates age-adjusted index scores for five neurocognitive domains, which are used to calculate a Total Scale Index score using norm tables for each Index scores in [Appendix 5.9](#). The algorithm (by vendor) to derive index scores is based on the current actual age of the participant at that visit. For longitudinal analyses this approach creates artificial variability. As a consequence, the derived data for index scores will not be used in the analyses, but will be derived from source data using the age at baseline for adjustment for all assessments. The algorithm to derive the Index scores using age at baseline will be described in the programming specifications (PDS) of this study.

A higher RBANS score indicates better cognitive function.

Mini Mental State Examination (MMSE)

The MMSE is a brief, practical clinician reported outcome that examines cognitive status ([Folstein et al., 1975](#)). It evaluates orientation, memory, attention, concentration, naming, repetition, comprehension, and the ability to create a sentence and copy two intersecting pentagons. The test consists of five domains (orientation, registration, attention, recall, and language) with a total score ranging from zero to 30. A higher score indicates better cognitive function. The five sub scores as well as the total score will be recorded.

Raven's Progressive Matrices

[figure not shown]
Raven's Progressive Matrices ([Raven et al 2000](#)) is a non-verbal, multiple choice measure of general ability and reasoning using a visual modality. It was designed to be culturally nonbiased, as neither language nor academic skills are required to answer items successfully.

Although all components of the Raven's Progressive Matrices Set A and Set B will be assessed, in order to calculate the APCC test score, only a subset of items from Sets A and B will be used (items A2, A4, A8, B1-B6), with a range from zero to nine.

Everyday Cognition scale (ECog-Subject and ECog-Informant)

The ECog scale measures cognitively-relevant everyday abilities and is comprised of 39 items covering six cognitively-relevant domains: Everyday Memory, Everyday Language, Everyday Visuospatial Abilities, Everyday Planning, Everyday Organization, and Everyday Divided Attention (Farias et al 2008). Within each domain, the ability to perform a specific task is rated on a five-point scale ranging from: 1) no difficulty, 2) mild difficulty, 3) moderate difficulty, 4) severe difficulty, or 5) unable to do. The scale has 2 versions one for patient (PRO) and one for informant (study partner).

The total score for the 39 items ranges from 39 to 195, with greater scores indicating worse daily function.

Biomarkers in Cerebrospinal Fluid (CSF)

The following AD related markers in CSF are analyzed:

- total-tau and phospho-tau (p-tau)
- $A\beta_{1-40}$, $A\beta_{1-42}$ and $A\beta_{1-42}/A\beta_{1-40}$

Biomarkers in blood: serum Light Chain Neurofilaments (NFL)

Available measurements for NFL from serum will be summarized.

Values below the lower limit of quantification (LLOQ) will be set to LLOQ/2 for statistical analysis, values above upper limit of quantification (ULOQ) will be imputed with ULOQ.

LLOQ and ULOQ value may differ across samples according to the dilution factor applied in the specific sample. For statistical analysis, the sample specific LLOQ and ULOQ value should be used.

[REDACTED]

[REDACTED]

Positron Emission Tomography (PET) Standard Uptake Value Ratio (SUVR)

Across the three F¹⁸ amyloid binding radiotracers used Florbetapir (FBP), Florbetaben (FBB) and Flutemetamol (Flute): Centiloids using the agreed formulae

For participants who consent to the voluntary AD-related imaging biomarker evaluations, regional activity concentration and the cortical Standardized Uptake Value (SUV) are measured based on the following brain regions of interest (ROIs):

- Parietal cortex
- Posterior cingulate or Precuneus
- Medial orbitofrontal cortex
- Anterior cingulate
- Temporal cortex

and the whole cerebellum as reference region.

Data for regional activity concentration will not be reported.

The *global* cortical amyloid load will be derived as the unweighted average cortical Standardized Uptake Value Ratio (SUVR) between the cortical ROIs and the reference region.

Standardization of Amyloid PET SUVR values

For Amyloid PET, the baseline load obtained from different tracers (florbetapir (FBP), flutemetamol (Flute) and florbetaben (FBB)) will be converted to a standardized Centiloid scale. The conversion equation for each tracer has been obtained following a non standard analysis method (AVID method) based on level-1 (GAAIN, Klunk et al. Centiloid values) and level-2 (InVicro Centiloid values) as documented in the Image Analysis charter from InVicro:

$$CL = 183.00 * SUVR_{FBP} - 176.97$$

$$CL = 123.90 * SUVR_{Flute} - 114.86$$

$$CL = 156.06 * SUVR_{FBB} - 148.132$$

The reference is [Klunk et al., 2015](#). The % change in SUVR will be calculated as

$$\%SUVR = \frac{(SUVR_{FU} - SUVR_{BL})}{SUVR_{BL}}$$

with $SUVR_{BL}$ as the baseline value and $SUVR_{FU}$ the SUVR value at follow-up visit.

Analysis of positive/negative amyloid levels

Amyloid level (positive/negative) is measured at screening by two methods:

- CSF collection via Lumbar puncture
- Brain Amyloid PET radiotracers (amyloid PET: SUVR)

The studies allow either method for determination of amyloid level. In cases both CSF A β and amyloid PET imaging tests are performed, at least one should be indicative of elevated brain amyloid. CSF samples are collected and analyzed using selected validated assay. The cut-off value to determine the amyloid level as positive/negative will depend on the assay selected. The criteria for positive amyloid level in CSF is based on pTau/Ab42 ratio. The criteria for positive amyloid PET will follow specifications for the specific radiotracer used. Following [Table 2-3](#) describes the cutoffs for both methods.

Table 2-3 Amyloid Level Stratification Criteria

Methods		Positive	Negative
CSF		
 • Elecsys ratio p-Tau/ Aβ1-42 > 0.024 AND 
 • Elecsys Aβ1-42 \leq 1700.0 pg/ml (upper limit of the measuring range) 	
 • Elecsys ratio p-Tau/ Aβ1-42 \leq 0.024 OR 
 • Elecsys Aβ1-42 > 1700.0 pg/ml (upper limit of the measuring range)
PET	Florbetapir (FBP)	SUVR_FBP \geq 1.1	SUVR_FBP < 1.1
	Flutemetamol (Flute)	SUVR_Flute \geq 1.123	SUVR_Flute < 1.123
	Florbetaben (FBB)	SUVR_FBB \geq 1.105	SUVR_FBB < 1.105

The same criteria will apply to all participants regardless of their genotype. In other words, both HMs and HTs were measured using either one of the methods (or both), and the positivity will be determined using the same rule in [Table 2-3](#). Analysis of Amyloid levels will be derived as Positive/Negative as described in [Table 2-3](#) above. However, in the database, eligibility result for Amyloid status will be Elevated/Not-Elevated as derived by vendor result (including a visual examination of the scan) or by the combination of the two results (whichever is Elevated) and this will be used only to check eligibility criteria for HT participants in this study.

2.7.2 Statistical hypothesis, model, and method of analysis

RBANS Total score and Index scores

Tables

RBANS total score and RBANS Index scores will be summarized on the SAF.

MMSE

Tables

MMSE total score and the sub-scores on each of the five domains (orientation, registration, attention, recall, and language) will be summarized on the SAF.

Raven's Progressive Matrices

Tables

Raven's total score (sum of all items from Sets A and B) and the sub-score included in the APCC (sum of items A2, A4, A8, B1-B6) will be summarized on the SAF.

Everyday Cognition scale (ECog-Subject and ECog-Informant)

Tables

ECog total score will be summarized on the SAF for participants as well as for informants.

[REDACTED]

[REDACTED]

[REDACTED]

Biomarkers in CSF

Tables

All available AD related markers will be summarized for actual values as well as for change from baseline.

Baseline ratios for p-Tau/A β 1-42 were used to determine Elevated /Not elevated brain Amyloid status and results will be reported as described in [Section 2.7.1](#).

Figures

Box-plots for CSF parameters (Total tau, p-tau, A β 1-40 and A β 1-42) and ratio A β 1-42/A β 1-40 over time by treatment group will be provided

Biomarkers in blood: serum Light Chain Neurofilaments (NFL)

Tables

Available measurements for NFL from serum will be summarized for actual values as well as for change from baseline.

Figures

Box-plots for serum NFL over time by treatment group will be provided

PET SUVR

Listing

PET SUVR listing will be reported.

Analysis of positive/negative amyloid levels

Tables

Amyloid levels (Positive/Negative) by method CSF and PET will be summarized as frequencies and percentages.

2.7.3 Handling of missing values/censoring/discontinuations

Due to the early termination of the trial, analyses of secondary efficacy variables will in general be based on observed cases only, i.e. there will be no imputation of missing data. Exception applies to missing data in RBANS Index scores, i.e., missing values for RBANS Index scores may be imputed using the imputation rule defined in [Appendix 5.1.3.3.1](#).

2.8 Safety analyses

Reporting of safety data will be based on the SAF. Safety assessments will include adverse events, serious adverse events, deaths, laboratory data (hematology, blood chemistry, urinalysis), vital signs, ECG, safety MRI, physical and neurological examination, prospective suicidality assessment, dermatology photo report.

Summary statistics for categorical data will typically include frequencies and percentages.

For safety parameters, the summaries will be based on worst available observation in an analysis window. The analysis window and definition of worst value is present in [Appendix 5.8](#).

2.8.1 Adverse events (AEs)

Treatment-emergent AEs (TEAEs) are events that either started after the first dose of study drug or events present prior to the start of study drug but increased in severity since the first dose. Adverse events reported within 31 days (5 half-lives) from study drug discontinuation date (i.e., last dose date) will be considered as TEAE. AEs reported more than 31 days after study drug discontinuation will not be considered treatment emergent (non-TEAE).

TEAEs and non-TEAEs will be summarized separately on the SAF.

Tables

TEAEs, SAEs, deaths and non-TEAEs will be summarized as follows

- TEAEs regardless of relationship to study drug by SOC, PT and maximum severity
- non-TEAEs, regardless of relationship to study drug by SOC and PT
- TEAEs causing study drug discontinuation by SOC, PT and maximum severity
- TEAEs related to study drug by SOC, PT and maximum severity
- TE-SAEs regardless of relationship to study drug by SOC and PT and maximum severity

Note: For missing information on AE relationship to study drug, the most conservative approach will be considered: If information on relationship of the AE to study drug is missing, the AE will be considered as related to study drug for reporting TEAEs.

The above summaries are generally without exposure adjustment, except from TEAEs by SOC and PT: this summary will be presented with exposure adjustment. The exposure-adjusted incidence rate of adverse events is defined as the number of participants with the adverse event divided by total participant years at risk in the treatment group. The time at risk for each participant will differ for each adverse event. For participants with events, only the time until the first event contributes to the total participant years at risk. For participants who do not experience the event, the time at risk will be calculated using the duration of exposure as defined in [Section 2.4.1](#). The exposure-adjusted incident rate will be summarized per 100 participant years. For participants with multiple occurrences of the same event, the event will be counted only once per participant.

Adverse events will be reported according to the latest MedDRA dictionary version available at the time of database lock.

If a participant reported more than one adverse event within the same PT, the adverse event with the greatest severity will be counted. If a participant reported more than one adverse event within the same SOC, the participant will be counted only once with the greatest severity at the SOC level, wherever applicable. Sorting order for the AE summaries will be as follows:

- For summaries by SOC, SOC will be presented in alphabetical order.
- For summaries by SOC and PT, SOC will be presented in alphabetical order; PT will be sorted within system organ class in alphabetical order.

Listings

All AEs will be listed ordered by country/center/participant and event date. Supplementary data for dermatological adverse events will also be listed (i.e., distribution of pruritus, presence, laterality and directionality).

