CNP520 appeared generally safe and well-tolerated in four Phase I studies and one Phase IIa study, with up to 3 months exposure, conducted in healthy adults ≥ 60 years of age. Clinical data generated to date have been collected in a total of 422 subjects that have been administered CNP520 (n = 335) or matching placebo (n = 87). Approximately two thirds (n = 213) of the subjects were ≥ 60 years of age, thereby reflecting the age group of the proposed study population. A total of 100 subjects ≥ 60 years of age have received CNP520 for 3 months. Approximately 30% of participants were carriers of at least one APOE $\epsilon 4$ allele.

The single maximum tolerated oral dose of 750 mg identified in healthy adults appeared to be safe and well-tolerated in healthy subjects ≥ 60 years of age. Multiple oral doses up to 300 mg q.d. (maximum dose tested) over 2 weeks and up to 85 mg q.d. (maximum dose tested) over 3 month appeared to be safe and well tolerated.

In healthy subjects ≥ 60 years of age, CNP520 reduced CSF A β concentrations in a dose-dependent manner by up to approximately 80% at the maximum single dose tested (750 mg) and 95% after multiple dosing at the highest dose tested (300 mg once a day (q.d)). A β_{40} concentrations in CSF decreased by 91% compared to baseline after three month exposure at CNP520 85 mg q.d.

CNP520 undergoes predominantly an oxidative metabolism via CYP3A4/5. Following three months of multiple dose administration of up to 85 mg CNP520 q.d., the mean terminal-half life was approximately 150 hours. CNP520 showed good brain penetration, indicated by cerebrospinal fluid (CSF) concentrations similar to the unbound plasma concentrations with both single and multiple dose administration.

Further details are provided in the CNP520 Investigator's Brochure (IB).

In October 2018, results of completed clinical trials evaluating other BACE inhibitors were made public:

- A Phase II study with elenbecestat showed a trend towards a positive effect on CDR-SB over placebo (p=0.55) in patients with MCI or mild to moderate AD ([Lynch et al 2018](#)).
- LY3202626 did not indicate a change in cognitive performance over the duration of the trial ([Lo et al 2018](#))

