5.6.5 Early study termination by the sponsor

Novartis may terminate the trial for reasons related to the benefit/risk assessment of treatment for participants in the study, or for regulatory or medical reasons (including slow enrollment) in consultation with the DMC. In the event that the study is terminated early, the HAs and IRBs/ECs will be informed on reasons for early termination and the process to prematurely withdraw the participants. In general, the participant should be seen as soon as possible and assessed as a prematurely withdrawn participant from the study. The withdrawal process may include additional procedures to be followed, in order to ensure that adequate consideration is given to the protection of the participant's interests.

6 Visit schedule and assessments

A preliminary step may be performed to obtain a buccal swab for APOE genotyping to be recorded in the local site database using the dedicated ICF#A. (refer to [Appendix 4](#))

[Table 6-1](#) lists all of the assessments and indicates with an “x” when the visits are performed.

Participants must be seen for all visits during the designated period, or as close to it as possible. Scheduled study visits during the treatment epoch may require multiple visits spread over different days that should be scheduled within the ± 4 -week window (exception for the cognitive assessments at month 3 XXXXXXXXXX, see [Table 6-1](#), footnote 45). Missed or rescheduled visits or assessments should not lead to automatic discontinuation. Upon study drug discontinuation, all dispensed investigational product should be reconciled.

Participants are encouraged to continue attending study visits even after study drug discontinuation. After the Early Termination of the treatment per the 11 July 2019 USM notification, mEoS visits can be scheduled any time after receipt of the Follow-up #2 notification but no later than 15-Mar-2020, and may be converted to a phone call in case of logistical constraints.

All adverse events and concomitant medications should be reconciled on the eCRF prior to End of Study (EoS).

Epoch	Screening ²							Treatment												
Visit Name	Scr1	Scr2	Scr3	Scr4	Scr5	Scr6	Scr7	Bas	Y1Q1 ₃₉	Y1Q2	Y1Q3	Y1Q4	Y2Q1	Y2Q2	Y2Q3	Y2Q4	Y3Q1	Y3Q2	Y3Q3	Y3Q4
Visit Numbers	101	102	103	104	105	106	107	201	202	203	204	205	206	207	208	209 ⁴⁰	210	211	212	213
Weeks									13	26	39	52	65	78	91	104	117	130	143	156
CDR, ECog ^{19,21,20,18}			X							X		X		X		X		X		X

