7.2.2 SAE reporting

To ensure participant safety, every SAE, regardless of causality to study treatment or to genetic or amyloid disclosure, occurring after the participant has provided informed consent and until 30 days after the last study visit/EOS or PPW must be reported to Novartis safety within 24 hours of learning of its occurrence. Any SAEs experienced after the 30 day period after the last study visit/EOS or PPW should only be reported to Novartis safety if the investigator suspects a causal relationship to study treatment.

All follow-up information for the SAE including information on complications, progression of the initial SAE and recurrent episodes must be reported as follow-up to the original episode within 24 hours of the investigator receiving the follow-up information. An SAE occurring at a different time interval or otherwise considered completely unrelated to a previously reported one must be reported separately as a new event.

Information about all SAEs (either initial or follow up information) is collected and recorded in English in the electronic Serious Adverse Event Report (eSAE) Form within the Oracle Clinical/Remote Data Capture (OC/RDC) system (whenever available and/or feasible) or on the paper SAE Report Form that should be used as back-up, especially in cases where there is no feasibility of the use of an eSAE Form. The investigator must assess the relationship of each SAE to CNP520.

SAEs (initial and follow-up) that are recorded electronically in the OC/RDC system should be entered, saved and e-signed within 24 hours of awareness of the SAE or changes to an existing SAE. These data will automatically be submitted to Novartis Chief Medical Office and Patient Safety (CMO&PS) immediately after investigator signature or 24 hours after entry, whichever occurs first.

Follow-up information is submitted as instructed in the investigator folder. Each re-occurrence, complication, or progression of the original event must be reported as a follow-up to that event regardless of when it occurs. The follow-up information should describe whether the event has resolved or continues, if and how it was treated, whether the blind was broken or not, and whether the participant continued or withdrew from study participation.

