9.5.2 Safety variables

All safety analyses will be carried out using the SAF. Descriptive summary tables will be provided by treatment for AEs, safety MRI and other safety parameters.

AEs, SAEs and Death

The number (and proportion) of participants with treatment-emergent AEs (events that started after the first dose of study medication or events present prior to the start of double-blind treatment but increased in severity based on preferred term) will be summarized in the following ways:

- by treatment, primary system organ class, and preferred term
- by treatment, primary system organ class, preferred term, and maximum severity
- by treatment, Standardized MedDRA Query (SMQ), and preferred term

Separate summaries will be provided for SAEs, death, and study medication related AEs, AEs leading to discontinuation and AEs leading to dose adjustment.

Laboratory data

Summary statistics of change from baseline laboratory results will be provided over time by treatment arm. These descriptive summaries will be presented by laboratory test category, visit, and treatment arm.

Shift tables will also be provided in which the normal laboratory ranges will be used to evaluate whether a particular laboratory test value is normal, low, or high for each visit relative to whether or not the baseline value is normal, low, or high. The shift from baseline to the most extreme post-baseline value will also be summarized. These summaries will be presented by laboratory test category, treatment and time (if applicable).

The number and percentage of participants with clinically notable laboratory results after baseline will be presented. The most extreme post-dose value is considered. Only participants with laboratory results at baseline and post-baseline from the central laboratory are included in the tabulations.

The number and percentage of participants with predefined liver enzyme abnormalities occurring during the study will be summarized by treatment arm.

Vital signs

Summary statistics of change from baseline values will be presented by vital sign parameter and treatment arm. Number and percentage of participants with clinically notable vital sign changes from baseline will be tabulated by treatment arm.

[figure not shown]
Electrocardiogram (ECG)

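### SAP 2.8.1 tabulates on-study SAEs only up to 31 days after last dose, so later non-fatal SAEs are not compared between arms as serious events

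*SAP*

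**What the plan says.** **Protocol.** Section 9.5.2 counts an AE as treatment-emergent if it began after first dose, or was present before and became more severe. It sets no end to that period. It then adds: "Separate summaries will be provided for SAEs, death, and study medication related AEs, AEs leading to discontinuation and AEs leading to dose adjustment". Section 7.1 collects AEs from consent to end of study. Section 7.2.2 extends SAE collection: every SAE "until 30 days after the last study visit/EOS or PPW must be reported to Novartis safety within 24 hours of learning of its occurrence". After the July 2019 stop, Section 6 says "mEoS visits can be scheduled any time after receipt of the Follow-up #2 notification but no later than 15-Mar-2020".

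**SAP.** Section 2.8.1 keeps the protocol's start rule and adds an end: "Adverse events reported within 31 days (5 half-lives) from study drug discontinuation date (i.e., last dose date) will be considered as TEAE". Anything later is classed as follows: "AEs reported more than 31 days after study drug discontinuation will not be considered treatment emergent (non-TEAE". It continues: "TEAEs and non-TEAEs will be summarized separately on the SAF". The sentence that introduces the table list names SAEs without any time limit. The list itself has one SAE entry, "TE-SAEs regardless of relationship to study drug by SOC and PT and maximum severity". The non-TEAE entry is by SOC and PT, with no split by seriousness, severity or period. Section 2.8.2 tabulates and lists deaths with no treatment-emergent limit, and 2.8.1 also lists all AEs. Section 2.3.2 separately summarizes SAEs that the investigator relates to genetic or amyloid disclosure. Section 4, which records departures from the protocol's analyses, does not mention the 31-day limit.

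**The concern.** The trial was stopped for a safety signal. AE collection was kept at the modified end-of-study visit (mEoS) even when the cognitive and MRI assessments there were dropped in December 2019. Serious events after the drug has washed out are among the data that this follow-up can provide. If the one on-study SAE table closes at day 31, a reader of the report cannot see from any table whether late non-fatal serious events differ between CNP520 and placebo. They would have to be counted by hand from the AE listing. Because Section 4 is silent, a reader who expects the protocol's SAE summary would also not learn that the table covers a shorter period.

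**Working it through.** **1. The 31-day window.** SAP 2.8.1 equates 31 days with five half-lives. Protocol 1.1 says "the mean terminal-half life was approximately 150 hours". Then 5 × 150 h ÷ 24 = 31.25 days, so the SAP's figure reproduces. The window has a pharmacological basis; the issue is what is tabulated after it.

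**2. Time outside the window.** Inputs: immediate stop under the urgent safety measure of 11-Jul-2019 (Protocol, Amendment 03 rationale), second follow-up notification of 12-Dec-2019 (same place), and latest mEoS on 15-Mar-2020 (Protocol Section 6).

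- Window closes: 11-Jul-2019 + 31 days = 11-Aug-2019.
- mEoS on 12-Dec-2019: 123 days after the window closes.
- mEoS on 15-Mar-2020: 248 days after last dose, and 248 − 31 = 217 days outside the window (about 7.1 months).
- Adding the 30 days of SAE reporting after the last visit: 217 + 30 = 247 days.
- For comparison, a follow-up visit 12 weeks after last dose, as in SAP 1.1.1: 84 − 31 = 53 days.

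**3. Where a late event goes.** Take an SAE first reported 100 days after last dose, in a participant still in follow-up.

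| Output | Included? | Shown as serious? |
|---|---|---|
| SAE table, SAP 2.8.1 | No, past day 31 | – |
| Non-TEAE table, SAP 2.8.1 | Yes | No |
| AE listing, SAP 2.8.1 | Yes | Not stated in the SAP |
| Deaths table and listing, SAP 2.8.2 | Only if fatal | Yes, as a death |
| Disclosure summary, SAP 2.3.2 | Only if related to disclosure | Yes |

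The table for adverse events of special interest in SAP 2.8.1.1 is also limited to treatment-emergent events.

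**4. Comparison with the protocol.** The SAE sentence in Protocol 9.5.2 can be read as covering all SAEs, or as covering treatment-emergent SAEs under that section's own definition. That definition has no end date, so a post-dose SAE at day 100 is included on either reading. SAP 2.8.1 excludes it, and Section 4 does not say so.

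**5. Pre-dose events.** An AE that starts between consent and first dose and does not worsen fails the TEAE definition. The only events the SAP explicitly calls non-TEAE are those reported more than 31 days after discontinuation. Whether pre-dose events enter the non-TEAE table is therefore undefined.

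**The case against.** The 31-day rule is not hidden. It appears in SAP 2.1.1 and 2.4.1 as well as 2.8.1, and it rests on five half-lives. Limiting the main SAE table to treatment-emergent events is a reasoned choice in an abbreviated report. Amendment 03 asks that changes due to early termination be documented in the SAP, not in Section 4 specifically. Output details are left to table shells that are not among the documents and might carry a seriousness or period split. These points stand. They explain the window, but they leave late SAEs without a table specified in the SAP.

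A reader might infer more than the text supports:

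- *That the non-TEAE table mixes late events with screening events.* The SAP does not say this. On its wording the table may hold only post-treatment events. The defect is a missing definition.
- *That off-drug SAEs are never compared between arms.* They are counted by treatment group in the non-TEAE table, and fatal ones are in the deaths table. What is missing is a comparison of them as serious events.
- *That nothing isolates the off-drug period.* The SAP has last-off-treatment summaries for cognition (2.5.1), volumetric MRI (2.5.2) and body weight (2.8.4.2).
- *That every participant has about seven months outside the window.* The 217 days are a maximum for one combination of dates. Footnote 43 to Protocol Table 6-1 places mEoS within 12 weeks of the treatment-completion visit, which would often be shorter. Participants already off drug in July 2019 but still attending could have longer.

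**Conclusion.** The point holds in a limited form. The one on-study SAE table in SAP 2.8.1 is narrower than that section's own introduction and than Protocol 9.5.2, and Section 4 does not record the difference. Non-fatal SAEs reported after day 31 are not compared between arms as SAEs. The follow-up affected is 123 to 217 days for a last dose on 11-Jul-2019 and an mEoS between 12-Dec-2019 and 15-Mar-2020; it varies by participant. The documents give no SAE incidence, so no count of affected participants is offered. The conclusion assumes that the table shells add no seriousness split that the SAP does not mention. This is a worthwhile, low-cost improvement to reporting. It does not imply that late events are lost, since they remain in the non-TEAE table and the listing.

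**What to change.** In SAP 2.8.1:

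1. Add an SAE table by SOC, PT and treatment arm for events more than 31 days after last dose. Alternatively, produce one SAE table from first dose to end of study with on-drug and off-drug columns.
2. State that the non-TEAE table covers post-treatment events only, and show any pre-dose events separately.
3. Declare the 31-day limit in Section 4 as a difference from Protocol 9.5.2.

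The cost is a few lines of SAP text and one or two extra tables. No new data are needed, and the treatment-emergent tables stay as they are.
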